6.4 Dose Modifications for Hypertension

- **Baseline blood pressure (BP)** is defined as the blood pressure obtained at the examination used for study enrollment. This baseline BP should be obtained as follows: 1) Obtain 3 serial blood pressures from the same extremity with the patient in the same position at rest with an appropriately sized cuff. Measures must be obtained at least 5 minutes apart. Avoid using the lower extremity if possible. 2) Average the systolic blood pressure from the 2nd and 3rd measurements. 3) Average the diastolic blood pressure from the 2nd and 3rd measurements. 4) The baseline BP is the average of the systolic over the average of the diastolic measurements.
- **Elevation** in either the systolic or diastolic blood pressure should be considered when following the algorithm below.
- **The upper limit of normal (ULN)** is defined as a BP equal to the 95th percentile for age, height, and gender. See [Appendix VIII](#).
- The NCI CTCAE will be utilized to determine the grade of hypertension for reporting purposes.
- Elevated BP measurements should be repeated on the same day to confirm the elevation. If confirmed, patients with elevated BP should have BP measurements performed at least twice weekly until BP is \leq ULN.
- The algorithm below will be used to manage ramucirumab- related hypertension.
- Hypertension should be managed with appropriate anti-hypertensive agent(s) as clinically indicated. It is strongly recommended that nephrology or cardiology be consulted in the evaluation and management of hypertension.

THIS PROTOCOL IS FOR RESEARCH PURPOSES ONLY, SEE PAGE 1 FOR USAGE POLICY

Elevations in BP are based on systolic or diastolic pressures.

[†] Elevated blood pressure (BP) measurements should be repeated on the same day to confirm the elevation. Patients with elevated BP at any time should have BP measurements performed at least twice weekly until BP is within the ULN.

[§] ULN (Upper Limit of Normal) is a BP equal to the 95th percentile from age, height, and gender-appropriate normal values (Appendix VIII).

^{*} If BP >25 mm Hg above ULN for age (verified) or Grade 4 HTN at any time, hold drug. Study drug should also be held for BP ≤ 25 mm Hg above the ULN age for > 14 days or 35 mmHg above baseline for > 14 days. Antihypertensive agents can be used to control hypertension as clinically indicated after study drug is held.

[^] Anti-hypertensive therapy should be prescribed as clinically indicated, including the use of multiple anti-hypertensive agents.

[#] Baseline BP is defined in Section 6.4.

Arm 1 of algorithm:

- If blood pressure (BP) ≤ 95% for age, height, and gender, continue ramucirumab at the same dose.

Arm 2 of algorithm:

- If BP ≤ 10 mm Hg above the ULN for age, height, and gender, continue ramucirumab at the same dose and recheck the BP within 72 hours.
 - If the BP is ≤ ULN on recheck, continue ramucirumab at the same dose.
 - If the BP remains above the ULN on recheck, then start antihypertensive therapy ([Section 7.7](#)) and follow Arm 3 of the algorithm from the point that anti-hypertensive therapy is started.

Arm 3 of algorithm:

- If BP is 11 to 25 mm Hg above the 95% for age, height, and gender on ≥ 2 of 3 measurements or > 35 mmHg above baseline on ≥ 2 of 3 measurements, start antihypertensive therapy ([see Section 7.7](#)), continue ramucirumab at the same dose, and monitor BP at least twice weekly.
 - If the BP returns to ≤ ULN within 14 days, continue ramucirumab at the same dose and continue anti-hypertensive therapy.
 - If the BP remains elevated ≤ 25 mm Hg above the 95% or > 35 mm Hg above baseline for more than 14 days after the institution of anti-hypertensive therapy, off protocol therapy.

THIS PROTOCOL IS FOR RESEARCH PURPOSES ONLY, SEE PAGE 1 FOR USAGE POLICY

hold ramucirumab, monitor BP at least every 3 days, and follow Arm 4 of the algorithm from the point that ramucirumab is held. The antihypertensive therapy should be continued until the BP is less than the ULN.

- If the BP returns to \leq ULN within 14 days, restart ramucirumab at a reduced dose ([Section 6.2](#)).
- If the BP remains $>$ ULN for more than 14 days, patient is Off Protocol Therapy.
- If the BP increases to > 25 mm Hg above the ULN despite anti-hypertensive therapy, **hold** ramucirumab, but continue the anti-hypertensive agent(s). Monitor the BP as clinically indicated and follow Arm 4 of the algorithm from the point that ramucirumab is held.
 - If the BP is \leq ULN within 14 days, ramucirumab may be restarted at a reduced dose ([Section 6.2](#)).
 - If the BP is $>$ ULN for > 14 days, the patient is Off Protocol Therapy ([Section 10.1](#)).

Arm 4 of algorithm:

- If BP is > 25 mm Hg above the 95% for age, height, and gender **hold** ramucirumab, monitor BP and administer anti-hypertensive therapy as clinically indicated.
 - If the BP returns to \leq ULN within 14 days, ramucirumab may be restarted at a reduced dose ([Section 6.2](#)).
 - If the BP is $>$ ULN for > 14 days, the patient is Off Protocol Therapy ([Section 10.1](#)).

Arm 5 of algorithm:

- If the participant develops Grade 4 hypertension, **discontinue** ramucirumab, monitor BP and administer anti-hypertensive therapy as clinically indicated. The patient is Off Protocol Therapy ([Section 10.1](#)).

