5.5.1.2 Dose-limiting hypertension

- Any Grade 4 hypertension
- A blood pressure > 25 mmHg above the 95th percentile for age, height, and gender ([Appendix VIII](#)) confirmed by repeated measurement is dose limiting.
- In patients who begin antihypertensive therapy a blood pressure > 10 mmHg but ≤ 25 mmHg above the 95th percentile for age, height, and gender ([Appendix VIII](#)) for > 14 days is dose limiting.

5.5.1.3 Non-hematological toxicity that causes a delay of ≥ 14 days between treatment cycles will be considered dose-limiting.

5.5.1.4 Proteinuria: Urine protein/creatinine (P/C) ratio > 1 and < 1.9 confirmed with a second measurement within 72 hours will be considered a DLT (See [Section 6.5](#))

5.5.1.5 Any gastrointestinal perforation event will be considered a DLT and require removal from protocol therapy.

5.5.1.6 Grade ≥ 2 wound complication or wound dehiscence will be considered a DLT and require removal from protocol therapy.

5.5.1.7 Grade ≥ 3 hepatic failure will be considered a DLT and require removal from protocol therapy.

5.5.1.8 Grade ≥ 2 reversible posterior leukoencephalopathy syndrome (RPLS) will be considered a DLT and require removal from protocol therapy.

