5.5.1.9 Grade ≥ 3 congestive heart failure will be considered a DLT and

THIS PROTOCOL IS FOR RESEARCH PURPOSES ONLY, SEE PAGE 1 FOR USAGE POLICY

require removal from protocol therapy.

5.5.1.10 Any toxicity that is possibly related to the study medication that requires removal from protocol therapy. Note: Allergic reactions that necessitate discontinuation of study drug will not be considered a dose-limiting toxicity.

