6.2 Dose Modifications for Non-Hematological Toxicity

- 6.2.1 Patients who have any dose-limiting non-hematological toxicity (as defined in [Section 5.5.1](#)) may continue on protocol therapy upon meeting eligibility lab requirements or baseline but should receive subsequent infusions at the next lower dose level, except as outlined in Sections [6.4](#) and [6.5](#). Doses reduced for toxicity will not be re-escalated, even if there is minimal or no toxicity with the reduced dose.

THIS PROTOCOL IS FOR RESEARCH PURPOSES ONLY, SEE PAGE 1 FOR USAGE POLICY

6.2.2 If the same non-hematological dose-limiting toxicity recurs after one dose reduction, the patient must be removed from protocol therapy.

6.2.3 Patients who have a dose-limiting non-hematological toxicity that does not resolve to baseline or eligibility criteria within 21 days after the planned start of the next treatment cycle must be removed from protocol therapy.

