10.0 CRITERIA FOR REMOVAL FROM PROTOCOL THERAPY AND OFF STUDY CRITERIA

10.1 Criteria for Removal from Protocol Therapy

- a) Clinical (including physical examination or serum tumor markers) or radiographic evidence of progressive disease (See [Section 12.0](#)).
- b) Adverse Events requiring removal from protocol therapy (See [Section 6.0](#)).
- c) Refusal of protocol therapy by patient/parent/guardian
- d) Non-compliance that in the opinion of the investigator does not allow for ongoing participation.
- e) Completion of 8 cycles of therapy.
- f) Physician determines it is not in the patient's best interest.
- g) Repeated eligibility laboratory studies (CBC with differential, bilirubin, ALT (SGPT) or serum creatinine) are outside the parameters required for eligibility prior to the start of ramucirumab (See [Section 8.1](#)).
- h) Study is terminated by Sponsor.
- i) Pregnancy

Patients who are removed from protocol therapy during cycle 1 should continue to have the required observations in [Section 8.1](#) until the originally planned end of the cycle or until all adverse events have resolved per [Section 13.4.4](#), whichever happens LATER. The only exception is with documentation of the patient's withdrawal of consent. Patients who are removed from protocol therapy in subsequent cycles should have the necessary observations to ensure adequate clinical care.

Patients who are off protocol therapy are to be followed until they meet the criteria for Off Study (see below). Ongoing adverse events, or adverse events that emerge after the patient is removed from protocol therapy, but within 30 days of the last dose of investigational agent, must be followed and reported via RAVE and CTEP-AERS (if applicable). Follow-up data will be required unless consent is withdrawn.

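### For Grade 4 hypertension the Section 6.4 footnote says hold and Arm 5 says discontinue; separately and less seriously, Protocol 11.2.1 and the analysis sets disagree on who is evaluable for DLT

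*Protocol*

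**What the plan says.** **Hypertension.** The algorithm footnote in Protocol 6.4 joins two states under one action. A verified pressure more than 25 mmHg above the upper limit of normal is one; the other is "or Grade 4 HTN at any time, hold drug".

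Arm 4 covers pressure more than 25 mmHg above the 95th percentile. The drug is held, and if pressure normalises within 14 days, "ramucirumab may be restarted at a reduced dose". Arm 5 opens "If the participant develops Grade 4 hypertension" and requires discontinuation and removal from protocol therapy.

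Two other sections bear on this. Protocol 6.2.1 says that children with a non-hematological DLT "should receive subsequent infusions at the next lower dose level, except as outlined in Sections" 6.4 and 6.5. Protocol 10.1(b) lists "Adverse Events requiring removal from protocol therapy" and refers the reader to Section 6.0.

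**Evaluability.** Under Protocol 11.2.1, a child without DLT who received less than 85% of the Cycle 1 dose is not evaluable, and is replaced, when the shortfall had a cause other than toxicity. The Dose Evaluable Set in Protocol 11.6.2 and the DLT-evaluable population in SAP Section 6 admit two groups only: children with a Cycle 1 DLT, and children with at least 85% of the dose and an adverse event assessment. Neither asks why a dose fell short.

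Protocol 6.3 requires permanent discontinuation after a Grade 3 or 4 infusion reaction. The note in Protocol 5.5.1.10 reads: "Allergic reactions that necessitate discontinuation of study drug will not be considered a dose-limiting toxicity".

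**The concern.** The first conflict is about patient safety. A hold and a discontinuation lead to different treatment: Arm 4 gives a held child a route back to the drug, and Arm 5 does not. With 12 mg/kg as the recommended dose, the next lower level in Protocol 5.3.1 is 8 mg/kg. A site that works from the footnote and Arm 4 could give that dose to a child whom Arm 5 has removed. This concerns Part B and any child still on treatment.

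The second is about bookkeeping. The rule for replacing children and the set used to evaluate a dose level should describe the same children. Here a child who stops early for a toxicity that is not a DLT is retained, by implication, under one text and excluded under the other two.

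**Working it through.** **1. Grade 4 hypertension: the texts side by side**

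| Source | State | Action | Restart? |
|---|---|---|---|
| 6.4 footnote | More than 25 mmHg above upper limit, or Grade 4 | Hold | Not stated |
| 6.4 Arm 4 | More than 25 mmHg above 95th percentile | Hold | Yes, reduced dose, if normal within 14 days |
| 6.4 Arm 5 | Grade 4 | Discontinue, off protocol therapy | No |

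- The two scales can overlap. Arm 4 is defined in mmHg, while 6.4 takes the grade from CTCAE. A child graded 4 can therefore also meet Arm 4's entry condition.
- Other sections do not break the tie. Section 6.2.1 defers to 6.4, and 10.1(b) defers to Section 6.0, which contains both instructions.
- Section 5.5 does not help. Items 5.5.1.5 to 5.5.1.9 each state that the event is a DLT and also requires removal. The Grade 4 line in 5.5.1.2 makes the event dose limiting but says nothing about removal. Arm 5 is the only explicit requirement to remove.
- Effect on the DLT count: none. Attributable Grade 4 hypertension in Cycle 1 is a DLT under 5.5.1.2 and meets the first limb of 11.6.2 and of the SAP set, whether the drug is held or stopped.

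**2. Evaluability: dose fractions**

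Inputs: three equal infusions per cycle (Protocol 5.1), 12 mg/kg (5.3.1), so 36 mg/kg are planned; threshold 85% (11.2.1, 11.6.2, SAP 6).

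- Stopped during Day 1: at most 12/36 = 33.3%.
- Stopped during Day 15: at most 24/36 = 66.7%.
- Stopped during Day 29 with fraction x of that infusion given: (2 + x)/3 = 0.85 gives x = 0.55. The child falls below 85% only if less than 55% of that infusion was delivered.

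Apply each definition to a child stopped at Day 1 or Day 15 for an allergic Grade 3 or 4 reaction, with no DLT:

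- 11.2.1: below 85%, but because of toxicity, so outside the class to be replaced. The child stays evaluable by implication if monitoring was done. Section 10.1 asks for Cycle 1 observations to continue after removal.
- 11.6.2 and SAP 6: no DLT and below 85%, so excluded.

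**3. Size of the denominator difference**

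- Cohort of 6 with one DLT and one such child: 1/6 against 1/5.
- Cohort of 12 with three DLTs and one such child: 3/12 = 25.0% against 3/11 = 27.3%.
- Neither reaches the one-third limit in 11.2.2. At 12 it takes three excluded children: 3/9 = 33.3%.
- Part B places: 6/0.8 = 7.5, rounded up to 8, which matches the plan. That leaves 2 spare places, and each replacement uses one.

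**The case against.** **On hypertension.** Arm 5 is explicit and written for Grade 4. The footnote authorises no restart for Grade 4, and *hold* can be read as the immediate step before removal. The cross-references lead back to a section that contains Arm 5. The flowchart is not shown in the available text, so what the footnote's asterisk marks cannot be seen. Much of this stands: Arm 5 is probably the intent, and the error needs a site to give the footnote more weight than the arm. But the footnote does not call the hold provisional, and it ties Grade 4 to a state that can restart.

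**On evaluability.** Section 11.2.1 keeps these children by implication only. Both sets are stated to serve dose escalation, which Protocol 5.1 reports as complete. SAP 6.7 plans a DLT listing, for Phase 1a only, and not a rate. Excluding a child who received part of one infusion is also more cautious than counting that child as DLT-free, which would lower the apparent DLT rate. All of this stands. It makes the point minor and sets the direction of the fix.

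**Stronger readings that the documents do not support.**

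- A reader might infer that the Grade 4 conflict distorts the DLT count. It does not, because Grade 4 is a DLT under either instruction.
- A reader might infer that prolonged milder blood-pressure elevation, held under Arm 3, opens the same evaluability gap. The Arm 3 text reads both as removal and as hold. Removal for possibly related toxicity is a DLT under 5.5.1.10. A hold followed by a late third dose at 8 mg/kg gives (12 + 12 + 8)/36 = 88.9%, which is evaluable.
- A reader might infer that the 12 mg/kg recommendation is in doubt. Nothing in the documents shows that an affected child was enrolled in Part A.
- A reader might want a probability that such a child occurs. Section 9.1.8 gives a frequency band for infusion reactions without grade, so none is computed here.

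**Conclusion.** The main point holds: Protocol 6.4 contains two incompatible instructions for Grade 4 hypertension, and no other section settles which governs. It is a patient-safety inconsistency with no effect on DLT counts. Its frequency cannot be sized, since the documents give no Grade 4 rate. The consequence per child is possible re-exposure at 8 mg/kg where Arm 5 allows none.

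The evaluability mismatch is also real but minor. Per affected child it means a denominator of 5 instead of 6, or one of Part B's two spare places. One such child does not move a cohort of 6 or 12 across one-third. It bears on reporting and, only if the escalation set is also used there, on Part B's evaluable count.

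The example rests on two assumptions: that the reaction is classed as allergic, and that the note in 5.5.1.10 prevails over the general Grade 3 or 4 rule in 5.5.1.1, whose exclusions do not name infusion reactions. The note's unqualified wording supports the second.

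**What to change.** **Footnote, Protocol 6.4.** Replace the hold clause with: *BP >25 mmHg above ULN: hold drug (Arm 4). Grade 4 HTN at any time: discontinue; off protocol therapy (Arm 5).*

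**Evaluability.** Use one definition in Protocol 11.2.1, Protocol 11.6.2 and SAP Section 6. Include an explicit rule: *a child without DLT who is stopped early for an allergic reaction and receives less than 85% of the Cycle 1 dose is not counted as DLT-free and is replaced.* State in the same place how other non-DLT toxicities that cause a shortfall are handled, and whether the definition applies to Part B.

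**Cost.** One phrase in the footnote and a sentence in each of the three definitions. No new data or analyses are needed. Each replaced child in Part B uses one enrolment place.

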- ¹ Women of childbearing potential require a negative pregnancy test prior to starting treatment and before starting each subsequent cycle; sexually active patients must agree to use a highly effective method of contraception during protocol therapy and for at least 3 months after the last dose of ramucirumab. Abstinence is an acceptable method of birth control.
- ² Blood pressure will be measured with an appropriate sized cuff at rest. Blood pressure measurement will be repeated within the same day if the blood pressure (BP) is elevated (> the 95th percentile for age, height, and gender). Please note that 3 serial blood pressures should be obtained and averaged to determine baseline BP (See [Section 6.4](#)). If both BP measurements are >95th percentile for age, height, and gender, follow the guidelines in [Section 6.4](#). Patients with elevated BP at any time should have BP measurements performed at least twice weekly until BP is within the 95th percentile for age, height, and gender (See [Appendix VIII](#)).
- ³ If patients have Grade 4 neutropenia then CBCs should be checked at least every other day until recovery to Grade 3 or until meeting the criteria for dose limiting toxicity.
- ⁴ If patients develop Grade 4 neutropenia then CBCs should be checked every 3 to 4 days until recovery to Grade 3.
- ⁵ See [Appendix IX](#) for UPC rationale and calculation and [Section 6.5](#) for dose modifications if UPC > 1. If patient is being followed for prior proteinuria and UPC is obtained at the scheduled time points, urinalysis is not also required. If patient has proteinuria (urine protein/creatinine (P/C) ratio >1), a second measurement should be obtained within 72 hours.
- ⁶ Tumor Disease Evaluation should be obtained on the next consecutive cycle after initial documentation of either a PR or CR. Subsequent scans may restart 2 cycles after the confirmatory scan. Please note that for solid tumor patients, if the institutional investigator determines that the patient has progressed based on clinical or laboratory evidence, he/she may opt not to confirm this finding radiographically. For patients with CNS disease (Part B), ECHO gradient MRI sequences per institutional standards are required to evaluate for hemorrhage (See [Appendix X](#)).

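### Section 6.4 gives conflicting hypertension instructions for a child at or below the 95th percentile but more than 35 mmHg above baseline, most clearly after such a child has been treated under Arm 3

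*Protocol*

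**What the plan says.** All references are to the Protocol.

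- **6.4, Arm 1** depends on the percentile alone: "If blood pressure (BP) ≤ 95% for age, height, and gender, continue ramucirumab at the same dose".
- **6.4, Arm 3, entry** has two limbs joined by *or*. One is 11 to 25 mmHg above the 95th percentile. The other is "> 35 mmHg above baseline on ≥ 2 of 3 measurements, start antihypertensive therapy". Ramucirumab stays at the same dose at this stage.
- **6.4, Arm 3, first sub-bullet:** "If the BP returns to ≤ ULN within 14 days, continue ramucirumab at the same dose and continue anti-hypertensive therapy".
- **6.4, Arm 3, second sub-bullet** covers pressure that remains "> 35 mm Hg above baseline for more than 14 days after the institution of anti-hypertensive therapy, off protocol therapy". The text then runs on, after a page break, to "hold ramucirumab, monitor BP at least every 3 days, and follow Arm 4 of the algorithm". Restart after the hold is tested against the ULN only, at a reduced dose.
- **6.4, asterisked footnote** separately calls for a hold when pressure is 35 mmHg above baseline for more than 14 days. It does not restrict this to readings above the ULN.
- **8.1, footnote 2**, which governs the scheduled measurements: "If both BP measurements are >95th percentile for age, height, and gender, follow the guidelines in" Section 6.4.
- **5.5.1.2**, the hypertension DLT definition, sets its millimetre thresholds above the 95th percentile and has no baseline limb. **5.5.1.10** makes a DLT of "Any toxicity that is possibly related to the study medication that requires removal from protocol therapy". **5.5.1.3** does the same for a delay of 14 days or more between cycles.

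**The concern.** The arms use two yardsticks, percentile and change from baseline, and no visible text ranks them. A child can satisfy one yardstick and fail the other.

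At entry, Arm 1 says carry on while the baseline limb of Arm 3 says start antihypertensives. Within Arm 3, one sub-bullet judges recovery by the ULN and the next judges persistence by the rise from baseline, so the same readings can meet both.

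Two sites with identical readings could therefore act differently: one continues the dose, the other holds, reduces or removes. Hypertension is a recognized class effect of this drug, and tolerability in children with CNS tumors is a primary aim of Part B. A safety rule that contradicts itself weakens the consistency of dosing and of the toxicity record in a cohort of about six.

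**Working it through.** There is no plan figure to reproduce. The check asks whether the conflicting state can occur, what the text says in it, and what could follow.

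**1. When the state can occur.** It needs baseline + 35 < BP ≤ ULN, hence baseline < ULN − 35. ULN values are from Appendix VIII at the 50th height percentile. Either component counts under 6.4.

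| Age | Boys: ULN | Boys: baseline below | Girls: ULN | Girls: baseline below |
|---|---|---|---|---|
| 1 | 103/56 | 68/21 | 104/58 | 69/23 |
| 6 | 114/74 | 79/39 | 111/74 | 76/39 |
| 12 | 123/81 | 88/46 | 123/80 | 88/45 |
| 15 | 131/83 | 96/48 | 127/83 | 92/48 |
| ≥17 | 136/87 | 101/52 | 129/84 | 94/49 |

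The limits are very low in the youngest children and least restrictive in adolescents.

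**2. Entry.** Take a boy of 17 at median height (systolic ULN 136) with an illustrative baseline of 98. On treatment he reads 134. Then 134 ≤ 136 meets Arm 1, and 134 − 98 = 36 > 35 meets the baseline limb of Arm 3. Footnote 2 of 8.1 would not send him to 6.4, because 134 is not above 136. At entry, that favors Arm 1.

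**3. After entry through that gate.** The same boy first reads 136 + 11 = 147, confirmed. He is above the 95th percentile and in the Arm 3 band, 147 − 98 = 49 above baseline. Antihypertensives start. Within 14 days he falls to 134 and stays there beyond day 14.

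- First sub-bullet: 134 ≤ 136 within 14 days, so continue at the same dose.
- Second sub-bullet and hold footnote: he has been 49 and then 36 above baseline, always more than 35, for more than 14 days, so stop or hold.
- Restart test if held: 134 ≤ 136, already met when the hold begins, with restart at a reduced dose.
- 5.5.1.2: not met. He was never more than 25 mmHg above the ULN, nor 11 to 25 above it for more than 14 days.

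**4. Exposure.** Both readings keep the dose unchanged for the first 14 days. After that, assume treatment at the stated RP2D of 12 mg/kg. The next lower level in 5.3.1 is 8 mg/kg, a fall of (12 − 8)/12 = 33.3% per infusion, and 6.2.1 bars re-escalation.

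If therapy starts at a Day 8 check, more than 14 days is reached on Day 23, before the Day 29 infusion.

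- Day 29 given reduced: (12 + 12 + 8)/36 = 88.9% of the Cycle 1 dose.
- Day 29 missed: 24/36 = 66.7%, below the 85% evaluability mark. Without a DLT, 11.6.2 would drop this child from the Dose Evaluable Set. Section 11.2.1 would not, because the shortfall is due to toxicity. The literal restart test does not force a missed infusion.

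**5. DLT.** On the hold text the child goes to Arm 4, where removal needs BP above the ULN for more than 14 days. This child does not meet that, so the hold forces neither removal nor a 14-day delay. The two readings give different DLT results only if the removal text applies (5.5.1.10) or the hold in fact delays a cycle by 14 days or more (5.5.1.3).

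If that happened, consider the chance of at least 2 DLTs among 6, with the other five at an assumed rate p that is not in the documents:

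- child not a DLT: 1 − (1 − p)^5 − 5p(1 − p)^4 = 2.3%, 8.1%, 26.3% at p = 5%, 10%, 20%;
- child a DLT: 1 − (1 − p)^5 = 22.6%, 41.0%, 67.2%.

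**The case against.** The best defense is that the protocol treats hypertension as pressure above the 95th percentile throughout. Footnote 2 of 8.1 calls a reading elevated only above that line. Section 7.7 and 5.5.1.2 use the same line, and Arm 3 speaks of pressure that returns to the ULN or remains elevated, which presupposes entry above it. The baseline limb would still do work on this reading: a child 1 to 10 mmHg above the ULN and more than 35 above baseline goes straight to Arm 3 instead of waiting for the Arm 2 recheck. The footnotes in 6.4 also appear to belong to a flow chart that is not shown in the text available here and that might set a priority.

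Most of this stands for entry, but it does not reach the child already in Arm 3. There the two sub-bullets use different yardsticks, and the hold footnote carries the baseline limb without the word elevated. If the flow chart does rank the arms, the written arms should agree with it.

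A reader might infer that the DLT count depends directly on which arm is read. The documents do not support that: the hold path leads to no DLT by itself. Removal rests on three words just before a page break, which may be a product of text extraction and which raise a separate conflict between removing and holding. A move from 1/6 to 2/6 also needs another DLT to be present already.

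**Conclusion.** The concern holds as a conflict of instructions. Its clear core is the child in Arm 3 who has come down to the ULN but remains more than 35 mmHg above baseline. At entry the overlap exists on the wording, but 8.1 footnote 2 largely answers it.

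The size is modest. The state needs a low baseline, a large rise that persists beyond 14 days on antihypertensives, and pressure at or below the ULN. The documents give no distribution of baseline pressure, so no frequency can be stated. Where it occurs, the difference is between an unchanged dose and a hold with restart one level down, after day 14 only. A DLT difference is possible but conditional.

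Two further inferences go too far. One is that the Part A result is in doubt: escalation is complete and the RP2D is stated, and nothing in the documents shows that such a child was enrolled. The forward effect is on Part B, with 6 evaluable patients and possibly 12. The other is that the missing baseline limb in 5.5.1.2 is an error: a DLT definition may be narrower than a management rule.

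The conclusion assumes that the flow chart contains no priority rule.

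**What to change.** Decide on one rule for pressure at or below the 95th percentile and more than 35 mmHg above baseline, and state it consistently in:

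- Arm 1;
- Arm 3: entry, the two 14-day sub-bullets and the restart test;
- the hold footnote in 6.4, and the flow chart if it differs;
- 8.1 footnote 2.

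The arms should be mutually exclusive, or the text should say which one governs. The clinical action is for the sponsor to choose; these passages need only be reconciled. No change to the DLT definition in 5.5.1.2 is required.

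The cost is a wording amendment. Baseline blood pressure is already recorded, so no new measurement is needed.
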